Official Title: Fundus Finding and Thiol-Disulfide Homeostasis in Gestational Diabetes

ClinicalTrials.gov Identifier: NCT05958927

Document Date: April 13, 2023

Statistical analysis

NCSS (Number Cruncher Statistical System) 2007 (Kaysville, Utah, USA) program will be used. While evaluating the study data, the distribution of the data will be evaluated with the Shapiro-Wilk Test, as well as the descriptive statistical methods (Mean, Standard Deviation, Median, Frequency, Ratio, Minimum, Maximum). Mann-Whitney U test will be used in comparisons of two groups that do not show normal distribution of quantitative data, and Student's t test will be used in case of normal distribution. Chi-square analysis will be used to determine the relationship between qualitative data. In order to determine the relationship between quantitative data, Pearson correlation analysis will be used in case of normal distribution and Spearman's correlation

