Official Title: Fundus Finding and Thiol-Disulfide Homeostasis in Gestational Diabetes

ClinicalTrials.gov Identifier: NCT05958927

Document Date: April 13, 2023

Study Protocol

This is a prospective case-control study conducted in 26 pregnant patients diagnosed with impaired glucose status (gest DM, IGT, high 50 gr GTT level) at 24-28 weeks of pregnancy and 34 healthy pregnant women with normal glucose status in the Uşak Training and Research Hospital Gynecology and Ophthalmology clinic.

A total of 60 pregnant women participated in the study. (26 gestational diabetes and 34 healthy pregnant women). Investigators excluded patients with type 1 diabetes mellitus and type 2 diabetes mellitus, patient that history of ocular surface disease, topical/systemic medical therapy, with ocular inflamatuar disease such as üveitis. The patients who is healthy pregnant and gestasional diabetes mellitus pregnant were recruit to this study. Controls group included only healthy pregnant.

All patients underwent a comprehensive ophthalmologic examination that included best-corrected visual acuity, slit-lamp examination, dilated fundus examination and applanation tonometry. Optic nerve retinal nerve fiber thickness and macular thickness were measured with OCT device in all patients

Tears analysis is less invasive, safe and acceptable method for research. Tear samples, Schirmer paper strips were placed in the lower conjunctival fornix of the right eye for a maximum of 5 minutes. Care was taken not to use tear stimulation, topical anesthetic or other eye drops. Attention was paid to factors such as lighting and room temperature. The ocular surface was not damaged. Tear samples were collected by a single individual (SD). A 15-20 mm test result was considered as enough for biochemical analysis. Schirmer strips were diluted with 500 μ l previously cooled PBS (phosphate-buffered saline), and stored in Eppendorf tubes until analysis (-80°C).

At the end of the study, fundus findings and tear oxidative stress values of both groups will be compared. ELISA method will be used for determination of tear oxidative stress findings.

The study followed the tenets of the declaration of Helsinki and was approved by the Uşak üniversitesi Ethics Committee (13.04.2023 / 93-93-04). Written and informed con-sent of participants was obtained for each patient prior to the study.

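### The available SAP text compares two non-randomised groups, with no matching described, only by unadjusted t or Mann-Whitney tests, so an outcome-related difference in maternal age or BMI would bias the comparison

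*SAP*

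**What the plan says.** The protocol describes its design thus: "This is a prospective case-control study conducted in 26 pregnant patients diagnosed with impaired glucose status". The comparison group is 34 healthy pregnant women, so membership follows glucose status. No matching is described.

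The exclusions begin: "Investigators excluded patients with type 1 diabetes mellitus and type 2 diabetes mellitus, patient that history of ocular surface disease". They go on to topical or systemic therapy and ocular inflammatory disease. None concerns age or BMI.

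The stated purpose is that "fundus findings and tear oxidative stress values of both groups will be compared". At least two sets of outcomes are quantitative:
- OCT: "Optic nerve retinal nerve fiber thickness and macular thickness were measured with OCT device in all patients".
- Tears: "ELISA method will be used for determination of tear oxidative stress findings".

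The SAP checks distributions with Shapiro-Wilk and then chooses between two tests: "Mann-Whitney U test will be used in comparisons of two groups that do not show normal distribution of quantitative data", and Student's t for normal data. That sentence is complete. Chi-square tests and pairwise correlations follow. The available text ends in the correlation sentence, just after "Pearson correlation analysis will be used in case of normal distribution and" and the naming of Spearman's method. Up to that point it mentions no regression, ANCOVA, stratification or other adjustment.

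**The concern.** Groups formed by glucose status have no built-in balance on other characteristics. If age or BMI differs between the groups and is also related to, say, macular thickness or a tear marker, the unadjusted difference contains that contribution. Neither planned test can separate it from a difference linked to glucose status. The planned correlations relate pairs of variables and do not adjust the group comparison.

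The group contrast is the study's stated purpose, so a significant result would naturally be read as a finding about glucose status. Both conditions are needed for bias: imbalance between groups and a relation to the outcome. If either is absent, the unadjusted comparison is sound in this respect.

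**Working it through.** **Inputs from the documents.** Group sizes 26 and 34. Their sum, 26 + 34 = 60, agrees with the protocol's total. The available text has no sample-size derivation, alpha, SD or effect size to reproduce.

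**Assumed inputs.** Two-sided alpha of 5%; r, the within-group correlation of covariate and outcome; D, the group difference in the covariate in SD units; no true difference by glucose status.

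**Step 1, bias.** With the outcome's within-group SD set to 1, one covariate shifts the unadjusted difference by r × D. Independent covariates acting in the same direction add up.

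**Step 2, false-positive rate of the t test.** Degrees of freedom are 26 + 34 − 2 = 58. The noncentrality is bias × √(26 × 34/60) = bias × 3.838. The rate is the two-tailed rejection probability of the noncentral t distribution.

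| Case | Bias (SD) | Noncentrality | False-positive rate |
|---|---|---|---|
| balanced or unrelated | 0 | 0 | 5.0% |
| r=0.2, D=0.3 | 0.06 | 0.230 | 5.6% |
| r=0.2, D=0.5 | 0.10 | 0.384 | 6.6% |
| r=0.3, D=0.5 | 0.15 | 0.576 | 8.7% |
| r=0.3, D=0.8 | 0.24 | 0.921 | 14.8% |
| two covariates, r=0.2 each, D=0.3 | 0.12 | 0.461 | 7.4% |
| two covariates, r=0.2 each, D=0.5 | 0.20 | 0.768 | 11.7% |

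**Step 3, Mann-Whitney branch.** Simulation on a log-normal outcome (40,000 runs per case) gives 5.2%, 6.6%, 8.5% and 14.3% for the four single-covariate cases with non-zero bias. The choice of test does not change the picture.

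**Step 4, after adjustment.** In simulation, linear regression on group plus the covariates gives 5.0% to 5.1% in the one- and two-covariate cases (100,000 runs each). On the log scale for the skewed outcome it gives 4.8% to 5.1%. In these simulations the modelled covariates are the only confounders and the model form is correct.

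**Step 5, cost in precision.** With age and BMI both imbalanced by 0.8 SD, the simulated ratio of adjusted to unadjusted standard error is 1.061 (r=0.3 each) or 1.160 (r=0.1 each). The unadjusted difference detectable with 80% power is about (1.96 + 0.84)/3.838 = 0.73 SD by normal approximation. It becomes 0.73 × 1.061 = 0.77 SD or 0.73 × 1.160 = 0.85 SD.

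**The case against.** The strongest reply is that the point rests on an absence in a text that is itself cut off. The SAP moves from descriptive statistics to two-group tests, chi-square and correlations, and a multivariable step could follow where the text ends. That stands. A reader might infer that the plan omits adjustment, but the documents support only the statement that the available text contains none.

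Second, neither document mentions age or BMI or says that they differ between the groups. A reader might infer that the comparison is confounded; there are no baseline data to show it. The choice of these two covariates is the reviewer's judgement, and every r and D above is assumed. At the weak end the departure from 5% is minor. Even the 0.15 SD bias behind the 8.7% is about a fifth of the 0.73 SD detectable difference.

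Third, a reader might add gestational week as an uncontrolled confounder. The protocol's wording, "high 50 gr GTT level) at 24-28 weeks of pregnancy and 34 healthy pregnant women with normal glucose status", places the window beside the cases but can be read as covering both groups. Week therefore does not belong in the default model. Including it has a price: three covariates imbalanced by 0.8 SD and unrelated to the outcome raise the standard error by about 25%.

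Fourth, adjustment is not a guarantee. The near-nominal rates hold only if no other confounder is at work and the model is right. The exclusions do already control some confounding by restriction, and the protocol states no causal conclusion, only a comparison.

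What remains is that the group-comparison sentence is complete, names only unadjusted tests, and no described design feature controls age or BMI.

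**Conclusion.** The point holds as a conditional risk. In the available text nothing in design or analysis controls a group difference in maternal age or BMI, and such a difference would bias the comparison of any quantitative outcome to which it is related.

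Its size cannot be known from the documents. Under the assumed values it runs from nothing (5.0%), through minor (5.6% to 6.6% at r=0.2, D=0.3 to 0.5), to material (8.7% at r=0.3, D=0.5; 14.8% at r=0.3, D=0.8). The conclusion assumes that no adjusted analysis stands in SAP text that is not available. It is a reason for an inexpensive improvement to the analysis, and it does not show that the planned comparison is wrong.

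**What to change.** Unless adjustment is already planned in text that is not available, add to the SAP before the groups are compared:

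- For each quantitative outcome, a linear regression on group plus maternal age and BMI, on the log scale if the outcome is skewed.
- The adjusted group difference with its 95% CI, reported beside the planned t or Mann-Whitney result. Base any statement about glucose status on the adjusted estimate.
- Gestational week at examination as a further covariate only if the controls were not confined to 24-28 weeks.
- Chi-square results labelled unadjusted in any case. If age and BMI cannot be retrieved, label the quantitative comparisons unadjusted as well.

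The cost is SAP wording and a few lines of analysis. This assumes that age and BMI can be taken from the antenatal record, since the protocol does not list them as recorded. The statistical price is the loss of precision shown in the working: a standard error about 6% to 16% larger if both covariates are imbalanced by 0.8 SD.

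### A Shapiro-Wilk pre-test chooses between Student's t and Mann-Whitney, and neither allows for unequal spread between 26 cases and 34 controls

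*SAP*

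**What the plan says.** The Statistical analysis section of the SAP states that "the distribution of the data will be evaluated with the Shapiro-Wilk Test". It then makes the choice of test depend on the result: "Mann-Whitney U test will be used in comparisons of two groups that do not show normal distribution of quantitative data", while "Student's t test will be used in case of normal distribution". No outcome has its test fixed in advance, and neither a transformation nor an unequal-variance test is mentioned.

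The Study Protocol describes a study "conducted in 26 pregnant patients diagnosed with impaired glucose status" and "34 healthy pregnant women with normal glucose status". It says that "fundus findings and tear oxidative stress values of both groups will be compared", and names no primary outcome.

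The available text gives no significance level, no level for Shapiro-Wilk, no statement of whether it is applied per group or pooled, and no expected mean, SD or skewness. The SAP text breaks off at the Spearman correlation. I do not count that as a fault, and a significance level may have stood in the lost part.

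**The concern.** Three features combine.

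- **The data choose the test.** With 26 and 34 women, Shapiro-Wilk cannot reliably detect mild skewness, so which test is used is partly chance. Skewed samples that happen to pass are not typical ones, and the t test is then applied to just those samples.
- **The two branches ask different questions.** Student's t compares arithmetic means, and Mann-Whitney compares the ordering of ranks. What is being estimated can change with the sample.
- **Neither branch allows for unequal spread.** I take Student's t to be the equal-variance test. Mann-Whitney also departs from its nominal level as a test of equal medians when spreads differ. The equal-variance t test over-rejects when the smaller group is the more variable. Here the cases are the smaller group, and they mix gestational diabetes, impaired tolerance and a high screening value, so wider spread is possible.

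At stake is the error rate of the tear comparison, one of the two comparisons the study exists to make.

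**Working it through.** The plan gives no figure to reproduce, so the rule was simulated.

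**Inputs from the documents.** 26 cases, 34 controls (26 + 34 = 60); Shapiro-Wilk; Student's t or Mann-Whitney.

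**Assumptions, not in the documents.** Two-sided 0.05 for the comparison and 0.05 for Shapiro-Wilk; log-normal values; null of equal geometric means (medians). Per-group reading: both groups must pass, otherwise Mann-Whitney (normal approximation, continuity correction). Pooled reading: one Shapiro-Wilk test on all 60 values.

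**Why unequal spread matters.** On the log scale, with SD 0.6 in cases and 0.3 in controls:

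- pooled variance = (25 × 0.36 + 33 × 0.09) / 58 = 11.97 / 58 = 0.206
- equal-variance SE² = 0.206 × (1/26 + 1/34) = 0.0140
- true variance of the difference = 0.36/26 + 0.09/34 = 0.0165
- SE ratio = √(0.0140 / 0.0165) = 0.92

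The equal-variance SE is about 8% too small before any pre-test enters. Student's t on logs accordingly rejects 7.0% to 7.5% at an SD ratio of 2. Welch's SE, √(s₁²/26 + s₀²/34), targets the true variance.

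**Null rejection rates (%)**, from repeated simulations of 12,000 to 40,000 data sets; a range shows the spread between runs:

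| Log SD, cases v controls | Rule, per group | Same, Welch in the t branch | Rule, pooled | Mann-Whitney fixed | Welch on logs |
|---|---|---|---|---|---|
| 0.4 v 0.3 | 6.5 | 6.0–6.1 | 5.4 | 5.5 | 5.0–5.3 |
| 0.5 v 0.3 | 7.4–7.6 | 6.8–7.0 | 6.0 | 6.2 | 4.9 |
| 0.6 v 0.3 | 8.0–8.8 | 7.4–7.8 | 7.2 | 7.0–7.4 | 4.6–5.5 |

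The largest run (40,000) gives 8.4 for the rule and 7.0 for Mann-Whitney in the last row. Monte Carlo SE at 8.4% is √(0.084 × 0.916 / 12,000) = 0.25 points, or 0.14 points at 40,000 runs, so the range in that row is noise.

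**Splitting the excess over 5%:**

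- 0.6 v 0.3: spread 7.0 − 5.0 = 2.0; per-group pre-test 8.4 − 7.0 = 1.4
- 0.5 v 0.3: spread 6.2 − 5.0 = 1.2; pre-test 7.4 − 6.2 = 1.2
- 0.4 v 0.3: spread 5.5 − 5.0 = 0.5; pre-test 6.5 − 5.5 = 1.0

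The split depends on skewness. At 0.4 v 0.2, where the t branch is reached more often, one run gives 9.2 for the rule and 6.7 for Mann-Whitney, so the pre-test adds 2.5. At 0.8 v 0.4 the figures are 7.4 and 7.0, so it adds 0.4.

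**Outside the main scenarios:**

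- SD ratio 3: 8.1% to 11.7% per group; at most 8.6% pooled.
- Identical distributions: 4.8% to 5.6%.
- Less variable cases (0.3 v 0.5): 5.1% for the rule and 5.1% for Welch on logs.
- Inside the t branch: with equal log SD 0.4 it is reached in about 20% of samples, with about 7% to 8% error; at 0.5 v 0.3 the error inside it is about 13%.
- True shift of 0.74 SD (log SD 0.4): power 78% to 79% for the rule against 80% for Welch on logs. Student's t and Mann-Whitney disagree on significance in about 9% of samples.

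**The case against.** The strongest reply is that the pre-test is the wrong culprit. When the two distributions are identical it adds at most about 0.6 points, and under pooled Shapiro-Wilk the rule does no worse than Mann-Whitney alone. Deleting the pre-test while keeping Mann-Whitney would leave 7.0% at 0.6 v 0.3. This stands, and it is why the remedy must also drop the equal-variance assumption. It does not clear the rule: under the per-group reading the switch adds to whatever unequal spread causes, and Welch inside the t branch removes only part of it.

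Second, the comparator is favoured by the set-up. Welch on logs is close to ideal for log-normal data with equal geometric means. For gamma data with equal medians it rejects 5.2% to 6.9% (the rule, per group: 6.1% to 9.0%). If the null is equal arithmetic means it rejects 6.4% to 67%. That also stands. The rule is no better on that null (20.1% against 17.6% at 0.6 v 0.3), but a reader should not infer that a log-scale analysis holds 5% in general. Student's t on logs does not hold it even for log-normal data.

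Third, nothing in the documents shows that tear values are skewed or that cases vary more. If the extra spread arises because some case subgroups are shifted, equal geometric means may not be the right null. The size of the problem is therefore conditional.

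**Conclusion.** The plan leaves the test to be chosen by the data, does not say how the choosing test is applied, and offers two candidates that both assume similar spread. Under the stated assumptions, with a more variable case group, the error rate is about 6.5% to 8.6% with per-group Shapiro-Wilk and about 5.5% to 7% with pooled, against about 5% for Welch on logs.

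A reader might infer that Shapiro-Wilk by itself causes the excess, or that 8.6% is a ceiling. Neither is supported. Unequal spread is the condition for nearly all of the excess. The upper figure moves with skewness, SD ratio and the reading of the rule, reaching about 12% at an SD ratio of 3 and falling to about 5% with equal spread. None of those inputs is in the documents.

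The point is worth acting on because the remedy is cheap and power is about equal. It does not show that the study's result would be wrong.

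**What to change.** Delete the Shapiro-Wilk decision rule and name one unequal-variance analysis per outcome before the data are examined:

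- tear oxidative stress values: Welch's t on log values, reported as a ratio of geometric means with its confidence interval;
- retinal nerve fibre and macular thickness: Welch's t on the measured scale;
- Mann-Whitney for all of these as a stated sensitivity analysis; Shapiro-Wilk and plots for description only;
- the significance level and sidedness, stated.

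The cost is SAP wording. Three consequences need accepting. Tear results become ratios of geometric means, not differences in arithmetic means; if the sponsor wants arithmetic means, the SAP should say so and use a raw-scale analysis instead. Error control is approximate if values are not log-normal (about 5% to 7% for gamma data). Zero or below-range assay values need a substitute stated in advance, because they cannot be logged.

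### Minor: the SAP uses Student's t test with no provision for unequal variances, so with 26 v 34 women its type I error drifts modestly if the spreads differ; Welch's test holds about 5%.

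*SAP*

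**What the plan says.** The SAP (Statistical analysis) sets one rule for all quantitative two-group comparisons. First, "the distribution of the data will be evaluated with the Shapiro-Wilk Test". If normality fails, "Mann-Whitney U test will be used in comparisons of two groups that do not show normal distribution of quantitative data". Otherwise Student's "t test will be used in case of normal distribution".

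No equal-variance check, unequal-variance version of the t test or significance level appears in the available text. The SAP text breaks off in the sentence on correlation, but the t-test clause before it is complete.

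The Protocol (Study Protocol, second paragraph) gives the group sizes as "26 gestational diabetes and 34 healthy pregnant women". It has no statistical section of its own.

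**The concern.** Student's t divides the mean difference by a standard error built from one pooled variance. Pooling gives the larger group more weight. If the smaller group has the larger SD, the pooled standard error is too small and the test rejects too often. If the smaller group has the smaller SD, the test rejects too rarely. With equal group sizes the effect nearly vanishes, so it is the 26/34 split that exposes the plan. Shapiro-Wilk cannot protect against this, because two normal samples with very different spreads both pass it.

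The same rule governs every normally distributed outcome, both the OCT thicknesses and the tear oxidative stress measures. If the spreads differ, p-values from the t-test branch do not have the error rate a reader will attach to them. One reason to guard against this is that the Protocol's first paragraph describes the cases as "26 pregnant patients diagnosed with impaired glucose status (gest DM, IGT, high 50 gr GTT level", a mixture of glucose categories, while the controls are all healthy. A mixed group may be more variable, and here it is also the smaller group, which is the direction that inflates false positives. That is plausible, not documented.

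**Working it through.** **Inputs from the documents.** n₁ = 26 cases and n₂ = 34 controls (26 + 34 = 60, which agrees with the stated total). The test is Student's t after Shapiro-Wilk. The plan gives no sample-size, power or error-rate figure to reproduce.

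**Assumptions, not in the documents.** Two-sided α = 0.05, normal data, equal true means, and the SD ratio r = case SD / control SD, varied because no SDs are given.

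**Step 1: why the error rate moves.** Set the control SD to 1.

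- True variance of the mean difference: V = r²/26 + 1/34.
- Average variance used by Student's t: P = [(25r² + 33)/58] × (1/26 + 1/34), where 1/26 + 1/34 = 0.06787.
- Large-sample type I error: 2Φ(−1.96 × √(P/V)).

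At r = 2:
- V = 4/26 + 1/34 = 0.1833
- P = (133/58) × 0.06787 = 0.1556
- √(P/V) = 0.922, so the error is 2Φ(−1.806) = 7.1%

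At r = 0.5:
- V = 0.25/26 + 1/34 = 0.0390
- P = (39.25/58) × 0.06787 = 0.0459
- √(P/V) = 1.085, so the error is 2Φ(−2.126) = 3.4%

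With 30 per group, P = V for every r, so to this order there is no drift.

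**Step 2: finite-sample values.** Step 1 ignores sampling variation in the two variances. The table averages over it: 2,000,000 draws of the sample variances, with the mean difference integrated analytically. Student's t uses 58 degrees of freedom. Welch's test uses the standard error √(s₁²/26 + s₂²/34) and Satterthwaite degrees of freedom.

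| Case SD / control SD | Student's t, 26/34 | Welch, 26/34 | Student's t, 30/30 |
|---|---|---|---|
| 0.5 | 3.52% | 5.00% | 5.16% |
| 0.667 | 3.98% | 4.99% | – |
| 0.8 | 4.39% | 4.98% | – |
| 1 | 5.00% | 4.99% | 5.00% |
| 1.25 | 5.71% | 5.00% | 5.02% |
| 1.5 | 6.32% | 5.00% | 5.07% |
| 2 | 7.23% | 5.01% | 5.16% |

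A separate numerical integration over a grid of the two variances gave the same 26/34 values to within 0.01 points. At ratios of 1/3 and 3 it put Student's t at about 3.2% and 8.2%.

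**Step 3: the whole SAP rule.** Shapiro-Wilk was applied to each group at an assumed 0.05 level, followed by the t test or Mann-Whitney (40,000 replicates, simulation error about ±0.2 points). About 90% of normal data sets reach the t-test branch.

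| Case SD / control SD | Rule with Student's t | Rule with Welch |
|---|---|---|
| 0.5 | 3.67% | 5.09% |
| 1 | 5.08% | 5.12% |
| 1.25 | 5.81% | 5.11% |
| 1.5 | 6.62% | 5.36% |
| 2 | 7.35% | 5.41% |

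The normality check does not remove the drift.

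**Step 4: power cost of Welch when the SDs are equal (26/34).**

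| Difference (SD units) | Student's t | Welch | Loss (points) |
|---|---|---|---|
| 0.5 | 47.12% | 46.97% | 0.15 |
| 0.6 | 61.98% | 61.82% | 0.16 |
| 0.745 | 80.29% | 80.15% | 0.14 |
| 1.0 | 96.52% | 96.47% | 0.05 |

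**The case against.** The best reply is that nothing in the documents shows the spreads to differ. If they are equal, Student's t is exact. For SD ratios between 0.8 and 1.25 the drift is only 0.6 to 0.7 points, and the larger figures need a two-fold SD difference, that is, a four-fold difference in variance. Student's t after a normality check is a recognised choice. The SAP text states no significance level, so no declared 5% rate is breached. In an unadjusted observational comparison of several measures, a shift of one or two points is unlikely to decide how a result is read. All of this stands, and it is why the point is minor and conditional.

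Two further cautions also stand. The SAP text is incomplete at its end, so the absence of a variance provision is a statement about the available text. And the Protocol describes a 15–20 mm Schirmer result as sufficient for biochemical analysis, so fewer than 60 tear samples may be analysable. The 26/34 figures assume that every woman contributes; a different split would change them.

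None of this removes the point. The test is chosen before the spreads are known, and the alternative holds its level whether or not they differ.

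**Conclusion.** The concern holds as a minor one. As written, the t-test branch keeps its nominal level only if the two groups have equal variances, and the plan neither checks nor allows for the contrary. At 26 v 34, for SD ratios between 0.5 and 2, the departure runs from 1.5 points too low (5.0 − 3.5) to 2.2 points too high (7.2 − 5.0). This rests on normal data, a two-sided 5% level and no missing samples, none of which the documents state. The actual SD ratio and its direction are unknown. Welch's test stays within 0.02 points of 5% across the same range.

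**What to change.** In the SAP's Statistical analysis section, replace Student's t test with Welch's unequal-variance t test for normally distributed outcomes. The Shapiro-Wilk and Mann-Whitney parts of the rule can stay as written. No preliminary test of equal variances is needed, because Welch's test is used whatever the spreads.

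The cost is one test name and 0.05 to 0.16 points of power at the differences tabulated above if the SDs are equal. The Mann-Whitney branch is untouched, so the complete rule would run at about 5.1% to 5.4% for ratios from 0.5 to 2, not exactly 5%.

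Welch's test does not settle who the 26 cases are. The Protocol's first paragraph lists three glucose categories and its second calls all 26 gestational diabetes; that needs reconciling separately.
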